8.5.3 Biomarkers

8.5.3.1 Additional biomarker assessments

8.5.3.1.1 Exploratory serum biomarkers

Serum samples will be collected for exploratory biomarkers.

Apart from hsCRP, as a general indicator of inflammation, no biomarkers are available which are validated and accepted to assess disease stage, severity, efficacy of treatments or stratification of HS patients for targeted treatments. Therefore, serum samples will be collected for exploratory biomarker assessments.

These exploratory samples will be biobanked and analyzed depending on results of the overall study outcome, other biomarker assessments in this study, and/or results from other studies and/or based on literature, new published results, or new internal results. The samples may be analyzed to support additional research to identify new HS therapies and to further understand HS pathobiology and that of other related diseases.

Further details on sample collection, numbering, processing and shipment can be found in the Laboratory Manual.

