
 To evaluate the safety and tolerability of secukinumab over 52 weeks of treatment. To explore the long-term effect of secukinumab with respect to HiSCR, AN count, proportion of patients with flares, HS related skin pain up to 52 weeks of treatment. To evaluate the effect of secukinumab with respect to the following efficacy assessments: 
 Modified Hidradenitis Suppurativa Score (mHSS); HS-Physician's Global Assessment (HS-PGA); 
 Dermatology Life Quality Index (DLQI); Health Status Questionnaire (EQ-5D-3L); Patient Global Impression of severity (PGI-s); Patient Global Impression of change (PGI-c); Work Productivity and Activity Impairment (WPAI); HS Symptom Diary; Inflammatory markers with respect to CRP and ESR compared to placebo after 16 weeks and in the two secukinumab dose regimens up to 52 weeks of treatment. To evaluate the pharmacokinetics of secukinumab in HS patients. To assess the development of immunogenicity against secukinumab. To explore the potential association of biomarker levels with secukinumab efficacy and safety by visit up to Week 52 visit (EOT2). 	
 Clinical safety and tolerability assessments: 
 physical exams, vital signs, laboratory assessments, AE monitoring Achievement of clinical response as defined by HiSCR. Absolute and percentage change from baseline in AN count. Flares Achievement of pain relief as defined by NRS30. Absolute and percent change from baseline in modified Hidradenitis Suppurativa Score (mHSS). HS-PGA response. HS-PGA response is defined as the achievement of at least a 2-point reduction in HS-PGA score compared to baseline. DLQI response and absolute/percent DLQI total score change from baseline. DLQI response is defined as a decrease greater than 5.0 points from baseline. EQ-5D-3L Categories on Category questions and summary statistics on EQ -5D -3L score questions. Patient Global Impression of severity and change (PGI-s and PGI-c) categories. Absolute and percent change from baseline in Work Productivity and Activity Impairment - Specific Health Problem (WPAI-SHP). HS Symptom Diary items score change from baseline. Absolute and percent change from baseline in CRP and ESR 
 AIN457 levels in serum anti-AIN457 antibodies levels in serum Biomarkers in serum

Objective(s)	Endpoint(s)

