12.6 Analysis of exploratory endpoints

For the exploratory endpoints analyses, the estimates of the differences between secukinumab groups versus placebo group and the corresponding p-values for pairwise comparisons will not be adjusted for multiple comparisons as no formal confirmatory hypothesis tests are planned.

Subpopulation Analysis

The number and percentage of HiSCR responders in bio-naive patients will be presented by visit up to end of study for each treatment group.

The number and percentage of HiSCR responders in patients with body weight lower and higher than 90kg (<90kg and \geq 90kg) will be presented by visit up to the end of study for each treatment group.

To allow for a pairwise comparison between the two secukinumab regimens and placebo at Week 16 in bio-naive patients, HiSCR at Week 16 will also be analyzed in bio-naive patients using logistic regression with treatment group, geographical region, Hurley stage, baseline AN count use of antibiotic, and baseline body weight as explanatory variables. Odds ratios will be computed for the comparison of secukinumab dose regimens versus placebo utilizing the logistic regression model fitted. In case of response rates of 0% or of 100% in one of the treatment groups, Fisher's exact test will be applied. Risk difference and confidence intervals for risk difference will be provided.

The subgroup analysis of patients with bodyweight lower and higher than 90 kg (<90kg and \geq 90kg) will be analyzed analogously to bio-naive patients.

Modified Hidradenitis Suppurativa Score

Summary statistics will be provided for absolute and percent change from baseline of modified Hidradenitis Suppurativa Score by visit up to end of study.

To allow for a pairwise comparison between two secukinumab regimens and placebo until Week 16, modified Hidradenitis Suppurativa Score up to Week 16 will also be analyzed using a MMRM with treatment group, the respective baseline value, Hurley stage, use of antibiotic, geographical region, baseline bodyweight, visit, baseline mHSS*visit interaction, and treatment group*visit as covariates, with unstructured covariance matrix.

HS-Physician's Global Assessment

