- To allow for a pairwise comparison between two secukinumab regimens and placebo until Week 16, DLQI score up to Week 16 will also be analyzed using a MMRM with treatment group, the respective baseline value, Hurley stage, use of antibiotic, geographical region, baseline bodyweight, visit, baseline DLQI*visit interaction, and treatment group*visit as covariates, with unstructured covariance matrix.

Work Productivity and Activity Impairment (WPAI)

Summary statistics will be provided for absolute and percentage change from baseline of WPAI component scores by visit up to end of study.

EQ-5D-3L

The EQ-5D is a questionnaire with 5 questions (regarding mobility, self-care, usual activities, pain/discomfort, and anxiety/depression) each with three categories (no problem, moderate problem, severe problems) and a health state assessment from 0 (worst possible health state) to 100 (best possible health state). The number and percentage of subjects in each of the three categories for each question will be presented by visit up to the end of study for each treatment group. Summary statistics will be shown for the health state assessment by visit up to the end of study for each treatment group.

PGI (PGI-s and PGI-c)

The number and percentage of subjects in each category will be presented by visit up to the end of study for each treatment group.

HS Symptom Diary

Summary statistics will be provided for absolute and percentage change from baseline of HS symptom component scores and the absolute HS symptom component score by visit up to end of study.

Inflammatory markers with respect to CRP and ESR

Summary statistics will be provided for absolute and percentage change from baseline of CRP and ESR by visit up to end of study.

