## **2 Statistical methods**

### **2.1 Data analysis general information**

Novartis will be performing the analysis. Statistical software SAS version 9.4 or later will be used.

Summary statistics for continuous variables will include N, mean, standard deviation, minimum, lower quartile, median, upper quartile, maximum. Summary statistics for discrete variables will be presented in contingency tables and will include absolute and relative frequencies. Unless otherwise stated, summary tables/figures/listings will be based on all subjects included in the population under consideration.

Listings will be presented by treatment arms.

Footnotes will generally be provided for:

- abbreviations used in the output; abbreviations used on several outputs, e.g. for listings in Appendix 16.2 can be presented on a separate page and do not have to be repeated as footnotes on each listing
- sorting order of categories, e.g. for sorting within MedDRA (Medical Dictionary for Regulatory Activities) hierarchy levels
- MedDRA version used for reporting of MedDRA coded data

Footnotes will generally NOT be given for

- units displayed on the output

- interpretation of results (e.g., “odds ratio larger 1 favors active treatment”)
- information that can be retrieved from the statistical section of the clinical study report (CSR) unless it is not identifiable from the output, e.g.
  - explanation of analysis model used unless results of more than one model are displayed in an output
  - derivations of variables (e.g. BMI will not be explained in a footnote)
- information that will be provided in the clinical study protocol and/or methods section of the CSR (e.g. baseline definition if this is specified in the statistical section of the CSR)

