### **CRP and ESR**

Summary statistics will be provided for absolute and percent change from baseline of CRP and ESR by visit up to Week 52 for each treatment group.

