## **5.4 Statistical models**

### **5.4.1 Analysis of continuous data**

Summary statistics (including N, mean, standard deviation, minimum, lower quartile, median, upper quartile, maximum) will be provided for continuous data by visit and treatment group. If applicable and not otherwise stated, means +/- SE will be plotted. If appropriate, summary statistics will also be derived for absolute and percentage changes from baseline.

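### CRP and ESR are meant to be compared with placebo at Week 16, but neither supplied document specifies that comparison

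*Protocol*

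**What the plan says.** The exploratory part of Protocol Table 2-1, repeated in SAP Table 1-1, lists "Inflammatory markers with respect to CRP and ESR compared to placebo after 16 weeks" and continues with the two regimens up to Week 52. The endpoint beside it is absolute and percent change from baseline. The rationale for Amendment 2 says the objective was added to explore a treatment effect on inflammatory markers.

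Protocol 8.5.3.1.1, on why serum is biobanked, shows the standing of one of the two markers: "Apart from hsCRP, as a general indicator of inflammation, no biomarkers are available which are validated and accepted to assess disease stage". This bears on relevance only; that section describes no CRP or ESR analysis.

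The analysis in Protocol 12.6 is one sentence: "Summary statistics will be provided for absolute and percentage change from baseline of CRP and ESR by visit up to end of study". SAP 2.13 matches it, with results shown per arm: "Summary statistics will be provided for absolute and percent change from baseline of CRP and ESR by visit up to Week 52". SAP Table 2-7, which assigns models to exploratory variables, has no row for CRP or ESR.

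The SAP defines what a summary contains, in 2.1: "Summary statistics for continuous variables will include N, mean, standard deviation, minimum, lower quartile, median, upper quartile, maximum". SAP 5.4.1 gives the same list. Geometric means are planned for drug concentrations (SAP 2.7), not for these markers.

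For mHSS and DLQI, Protocol 12.6 adds an MMRM, introduced with the words "To allow for a pairwise comparison between two secukinumab regimens and placebo until Week 16".

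**The concern.** The objective is comparative and the named analysis is not. Columns of per-arm summaries leave the reader to judge the drug effect by eye, with no estimate, no interval and no allowance for baseline differences. If someone later wants the comparison, its scale and model would be chosen after the data are seen.

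The scale matters because percent change has a floor at -100% and no ceiling. For a right-skewed marker its mean and SD are pulled up by a few patients. hsCRP is the marker the protocol sets apart from all other HS biomarkers, so it is a likely candidate for reporting.

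**Working it through.** **1. Objective against analysis.** The documents state no SD, effect size or power for CRP or ESR, so there is no planned figure to reproduce. The check is a comparison of texts.

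- Objective (Protocol Table 2-1): comparison with placebo at Week 16.
- Protocol 12.6 and SAP 2.13, CRP and ESR: summaries by visit. No contrast, interval, model or baseline covariate.
- Protocol 12.6, mHSS and DLQI: MMRM with treatment, baseline value, Hurley stage, antibiotic use, region, body weight, visit, and the baseline-by-visit and treatment-by-visit interactions.
- Placebo group: Protocol 12.1 pools the two placebo arms for Treatment Period 1. The efficacy groups in SAP 2.3.1 keep them apart, so a Week 52 SAP table built on those groups has no single placebo column at Week 16.

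**2. Effect of skewness on the planned summaries.** Assumptions, none from the documents: the marker is lognormal; the SD of the log value is s at both visits; the baseline to Week 16 correlation of log values is r; the placebo geometric mean does not change; the drug/placebo ratio of geometric means is g.

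The log change then has mean ln(g) and variance 2s²(1 - r), so:

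- mean percent change = 100 × (g × exp(s²(1 - r)) - 1)
- median percent change = 100 × (g - 1)

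For placebo, g = 1. With s from 0.8 to 1.2, r from 0.5 to 0.7 and g of 0.75 or 0.80, the two extremes for drug and a middle case are:

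| s, r, g | exp(s²(1 - r)) | Mean, drug | Mean, placebo | Median, drug | Median, placebo |
|---|---|---|---|---|---|
| 0.8, 0.7, 0.75 | exp(0.192) = 1.212 | -9% | +21% | -25% | 0% |
| 1.0, 0.5, 0.75 | exp(0.500) = 1.649 | +24% | +65% | -25% | 0% |
| 1.2, 0.5, 0.80 | exp(0.720) = 2.054 | +64% | +105% | -20% | 0% |

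The same factor multiplies both arms. The sign of the difference is therefore right in each row, but subtracting the means gives -30, -41 and -41 points where the true falls are 25%, 25% and 20%. With milder skew, s = 0.5, the factor is only exp(0.075) = 1.078 to exp(0.125) = 1.133, so placebo would show +8% to +13%.

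**3. What a specified contrast would give.** For an ANCOVA on log values with log baseline as covariate, SE = s × √(1 - r²) × √(2/n). Take n = 180 in each regimen and 180 in pooled placebo (Protocol Section 3), with complete data, so √(2/180) = 0.1054.

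- s 0.8, r 0.7, g 0.75: SE = 0.8 × 0.714 × 0.1054 = 0.060; 95% CI about 0.67 to 0.84.
- s 1.0, r 0.5, g 0.75: SE = 1.0 × 0.866 × 0.1054 = 0.091; 95% CI about 0.63 to 0.90.
- s 1.2, r 0.5, g 0.80: SE = 1.2 × 0.866 × 0.1054 = 0.110; 95% CI about 0.65 to 0.99.

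Each CI is g × exp(±1.96 × SE). This is the kind of result the objective asks for and the specified analysis does not produce.

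**The case against.** Several points on the other side stand.

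- **The summaries are not only means.** Medians and quartiles are planned, and under the model above the median recovers the true fall exactly. A reader might infer that the plan can report these markers only in distorted form. SAP 2.1 and 5.4.1 rule that out.
- **Placebo is inflated too.** A reader might infer that the table would make the drug look harmful. Under these assumptions drug is below placebo in every case, so a mean rise on drug misleads only if the placebo column is ignored.
- **No power is lost to a planned test.** A reader might compare the power of a t-test on percent change with that of a log-scale ANCOVA. Neither supplied document plans that t-test, and Protocol 12.6 plans no formal confirmatory tests for exploratory endpoints, so such a gap is not a consequence of the plan.
- **The Week 16 SAP was not available.** A reader might infer that no comparison is planned anywhere. SAP Section 1 describes that document as covering the primary and secondary objectives in the testing hierarchy, which does not include CRP and ESR. But the mHSS and DLQI models of Protocol 12.6 are also absent from the Week 52 SAP and are not listed as dropped in its Section 4, so Week 16 exploratory comparisons may be specified elsewhere.
- **Protocol 12.6 opens in general terms**, saying that "the estimates of the differences between secukinumab groups versus placebo group and the corresponding p-values for pairwise comparisons will not be adjusted". This suggests that differences are expected for exploratory endpoints. It names no scale or model for CRP or ESR, so it does not fill the gap.
- **Skewness is an assumption**, and the biobank section supports only the relevance of hsCRP; it contains no analysis of it.

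These points narrow the concern. They do not supply the missing Week 16 contrast.

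**Conclusion.** The concern holds as a mismatch between objective and analysis. CRP and ESR are to be assessed against placebo at Week 16, and the supplied documents specify only by-visit summaries, with no between-arm estimate, interval or baseline adjustment. Whether the Week 16 SAP closes the gap is open.

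The scale problem is conditional and confined to the mean and SD of percent change. It is large if log-SD is about 0.8 or more, small at 0.5, and does not touch the medians. The same formula would apply to ESR, but the documents give no distribution for either marker.

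Priority is low. The endpoint is exploratory and outside the testing hierarchy, and no primary or secondary conclusion, sample size or alpha depends on it.

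**What to change.** In Protocol 12.6 and the SAP:

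- Analyse log(hsCRP) and log(ESR) at Week 16, each regimen against pooled placebo, with the log baseline value and otherwise the same covariates as the mHSS and DLQI models. Report geometric mean ratios with 95% CI.
- Use an MMRM if the marker has several post-baseline visits up to Week 16, otherwise ANCOVA. hsCRP is part of the chemistry panel (Protocol 8.4.4.2.2), and Table 16-1 schedules chemistry at Weeks 2, 4, 8, 12 and 16. The rows for hsCRP and ESR could not be read in the available text of Table 8-1, so confirm both schedules.
- Add the geometric mean ratio to baseline to the by-visit summaries up to Week 52.
- Confirm that the rule setting laboratory values below the quantification limit to that limit (SAP 5.1.5) covers ESR, which is measured locally (Protocol 8.4.4.1.1), so that logs are defined.
- If the Week 16 SAP already contains such a contrast, cross-refer to it.

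The cost is one extra model per marker on data already being collected. If the sponsor does not want the model, rewording the objective as descriptive would also remove the mismatch, but would leave the placebo question without an estimate.

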8.5.3.1.2 Optional biopsy sampling substudy

The study includes an optional biopsy substudy which requires a separate informed consent signature if the patient agrees to participate. Only patients from sites with interest in the optional biopsy substudy will be invited to participate. Sites and patients are encouraged to participate in the study, given the importance of the related research and the need to reflect the variability of HS pathobiology.

Formalin-fixed paraffin-embedded (FFPE) lesion punch biopsy samples from baseline and on-treatment will be sent to the central laboratory. Detailed instructions on sample harvesting, preparation and storage will be provided in the Laboratory Manual.

Exploratory biopsy research will entail histology and transcriptomic. The intermediate products of gene expression, such as mRNA, will be used to examine gene expression signatures using suitable gene expression profiling techniques including next generation sequencing. This substudy may include, but is not limited to, analyses to gain a better understanding of the mechanistic aspects of HS. These data may also support the identification of pathways/markers that characterize the disease or response to treatment with secukinumab.

8.5.3.1.3 Optional DNA sampling

The study includes an optional DNA component which requires a separate informed consent signature if the patient agrees to participate. It is required as part of this protocol that the Investigator presents these options to the patient.

Exploratory DNA research studies are planned as a part of this study with the objectives of identifying genetic factors which may (1) predict response to treatment with secukinumab; (2) predict relative susceptibility to drug-drug interactions; (3) predict genetic predisposition to side effects; or (4) be related to HS or autoimmune diseases.

With the advances in technology over time, the most appropriate technology will be used at the time the exploratory DNA research is performed. This may include the study of the entire genome (whole genome sequencing).

Laboratory Manual will contain detailed information on sample collection, handling, and shipment.

8.5.4 Other Assessments

8.5.4.1 Trial feedback questionnaire

This trial will include an option for subjects to complete an anonymized questionnaire, referred to as a 'Trial Feedback Questionnaire'. This questionnaire will give subjects an opportunity to provide feedback on their clinical trial experience. Individual subject level responses will not be reviewed by investigators. Responses will be used by the sponsor (Novartis) to understand where improvements can be made in the clinical trial process. This questionnaire does not collect data about the subject's disease, symptoms, treatment effect or adverse events, and therefore is not considered trial data. Should any spontaneous information be collected about AEs, this will be transferred to the safety database.

8.5.4.2 Health Care Resource Utilization

Studies conducted in Canada and the United States have indicated the high economic impact of the disease both on a direct level (due to hospitalizations and emergency department visits) and on an indirect level (occupational disability). All-cause and HS-related outpatient visits, inpatient stays and emergency visits not planned per protocol will be collected to explore possible decreases in utilization of these resources. Health Care Resource Utilization will be entered on eCRF.

9 Study discontinuation and completion

9.1 Discontinuation

9.1.1 Discontinuation of study treatment

Discontinuation of study treatment for a subject occurs when study treatment is stopped earlier than the protocol planned duration, and can be initiated by either the subject or the investigator.

Subjects may voluntarily discontinue study treatment for any reason at any time.

The investigator must discontinue study treatment for a given subject if, he/she believes that continuation would negatively impact the subject's well-being.

Study treatment must be discontinued under the following circumstances:

- Subject's wish
- Withdrawal of consent
- Pregnancy
- Ongoing use of prohibited treatment as per the prohibited treatment [Section 6.2.2](#)
- Any situation in which study participation might result in a safety risk to the subject
- Following emergency unblinding

- Emergence of the following adverse events: any adverse events that in the judgment of the investigator/qualified site staff, taking into account the subject's overall status, prevent the subject from continuing study treatment (for example, sepsis)
- Any laboratory abnormalities that in the judgment of the investigator/qualified site staff, taking into consideration the subject's overall status, prevents the subject from continuing study treatment

If discontinuation of study treatment occurs, the investigator should make a reasonable effort to understand the primary reason for the subject's premature discontinuation of study treatment and record this information in the eCRF.

Subjects who discontinue study treatment should NOT be considered withdrawn from the study UNLESS they withdraw their consent (see Withdrawal of Informed Consent, [Section 9.1.2](#)). **Where possible, they should continue attending site visits for the assessments indicated** in the assessment schedule (including efficacy assessments). If the subject does not wish to attend any further visits, the subject should return to the site after discontinuation of study drug, for an End of Treatment (EOT) visit and Follow-up visit (F8). Assessments detailed in the EOT and Follow-up visit (F8) in [Table 8-1](#) should be completed and recorded in the eCRF. If the subject fails to return for these assessments for unknown reasons, every effort (e.g. telephone, e-mail, letter) should be made to contact the subject/pre-designated contact as specified in the Lost to Follow-up section ([Section 9.1.3](#)). This contact should preferably be done according to the study visit schedule.

If the subject cannot or is unwilling to attend any visit(s), the site staff should maintain regular telephone contact with the subject, or with a person pre-designated by the subject. This telephone contact should preferably be done according to the study visit schedule.

The investigator must also contact the IRT to register the subject's discontinuation from study treatment.

If discontinuation occurs because treatment code has been broken, please refer to Emergency breaking of treatment code section.

